4.4. End of Study Definition

A participant is considered to have completed the study if he/she has completed all phases of the study including the last visit or the last scheduled procedure shown in the [Schedule of Activities](#).

The end of the study is defined as the date of the last scheduled procedure shown in the [Schedule of Activities](#) for the last participant in the trial globally.

5. STUDY POPULATION

This study can fulfill its objectives only if appropriate participants are enrolled. The following eligibility criteria are designed to select participants for whom participation in the study is considered appropriate. All relevant medical and nonmedical conditions should be taken into consideration when deciding whether a participant is suitable for this protocol.

Prospective approval of protocol deviations to recruitment and enrollment criteria, also known as protocol waivers or exemptions, is not permitted.

5.1. Inclusion Criteria

Participants are eligible to be included in the study only if all the following criteria apply:

Age and Sex:

1. Male or female participants between the ages of 18 (or the minimum country-specific age of consent if >18) and 75 years, inclusive, at Screening.
 - Refer to [Appendix 4](#) for reproductive criteria for male ([Section 10.4.1](#)) and female ([Section 10.4.2](#)) participants.

Type of Participant and Disease Characteristics:

2. Participants who are willing and able to comply with all scheduled visits, treatment plan, laboratory tests, lifestyle considerations, and other study procedures.
3. Participants with a diagnosis of plaque psoriasis (psoriasis vulgaris) for at least 6 months prior to Baseline/Day 1 (prior to first dose of study drug).
4. Have a PASI score of 12 or greater AND a Physician Global Assessment score of 3 (“moderate”) or 4 (“severe”) at Baseline/Day 1 (prior to first dose of study drug).

CCI

Weight:

6. Body weight must be >40 kg.

Informed Consent:

7. Capable of giving signed informed consent as described in [Appendix 1](#), which includes compliance with the requirements and restrictions listed in the informed consent document (ICD) and in this protocol.
8. Must discontinue systemic, topical and/or phototherapy therapies (eg, ultraviolet B (UVB) or photochemotherapy (PUVA)) for the treatment of psoriasis per timing criteria described in [Section 5.2](#).

5.2. Exclusion Criteria

Participants are excluded from the study if any of the following criteria apply:

Medical Conditions:

1. Currently have non-plaque forms of psoriasis, eg, erythrodermic, guttate, or pustular psoriasis, except for nail psoriasis which is allowed.
2. Evidence of other skin conditions (eg, eczema) at the time of screening or baseline visit that would interfere with the evaluation of psoriasis.
3. Current drug-induced psoriasis, eg, a new onset of psoriasis or an exacerbation of psoriasis from beta blockers, calcium channel blockers, antimalarial drugs or lithium.
4. If receiving non-prohibited concomitant medications for any reason, must be on a stable regimen, which is defined as not starting a new drug or changing dosage within 7 days or 5 half-lives (whichever is longer) prior to first dose of study drug.
5. Any psychiatric condition including recent (within the past year) or active suicidal ideation or behavior that meets any of the following criteria:
 - a. Suicidal ideation associated with actual intent and a method or plan in the past year: “Yes” answers on items 4 or 5 of the Columbia suicide severity rating scale (C-SSRS) (10.9).
 - b. Previous history of suicidal behaviors in the past 5 years: “Yes” answer (for events that occurred in the past 5 years) to any of the suicidal behavior items of the C-SSRS.
 - c. In the opinion of the investigator or Sponsor (or designee) exclusion is required.
6. Have any condition possibly affecting oral drug absorption, eg, gastrectomy, clinically significant diabetic gastroenteropathy, or certain types of bariatric surgery such as gastric bypass. Procedures such as gastric banding, that simply divide the stomach into separate chambers, are NOT exclusionary.
7. Have current or recent (within the past year) history of severe, progressive, or uncontrolled renal, hepatic, hematological, gastrointestinal, metabolic, endocrine, pulmonary, cardiovascular, or neurological disease.
8. History of any lymphoproliferative disorder (such as Epstein-Barr virus [EBV] -related lymphoproliferative disorder, history of lymphoma, leukemia, or signs and symptoms suggestive of current lymphatic disease.
9. History (single episode) of disseminated herpes zoster or disseminated herpes simplex, or a recurrent (more than one episode of) localized, dermatomal herpes zoster.

10. History of infection requiring hospitalization, parenteral antimicrobial therapy, or as otherwise judged clinically significant by the investigator within 3 months prior to first dose of study drug or a history of infection requiring oral antimicrobial therapy within 2 weeks prior to first dose of study drug.
11. Infected with *Mycobacterium tuberculosis* (TB) (see [Section 8.2.1.1](#)).
12. Have known immunodeficiency disorder or a first-degree relative with a hereditary immunodeficiency.
13. History of recurrent (≥ 2) venous thrombosis or any arterial thromboembolism or known blood clotting disorders.
14. History of acute coronary syndrome (eg, myocardial infarction, unstable angina pectoris) and any history of cerebrovascular disease within 24 weeks before screening.
15. Have any malignancies or a history of malignancies except for adequately treated or excised non-metastatic basal cell or squamous cell cancer of the skin or cervical carcinoma in situ.
16. Have undergone significant trauma or major surgery within 1 month prior to Screening or plan to undergo surgery during treatment period.
17. Other acute or chronic medical or psychiatric condition including recent (within the past year) or active suicidal ideation or behavior or laboratory abnormality that may increase the risk associated with study participation or investigational product administration or may interfere with the interpretation of study results and, in the judgment of the investigator, would make the participant inappropriate for entry into this study. For any reason in the opinion of the investigator or sponsor, the participant is inappropriate for entry into this study.

Prior/Concomitant Therapy:

18. Planned initiation of, or changes to, concomitant medication that could affect psoriasis (eg, beta blockers, calcium channel blockers, antimalarial drugs or lithium) are to occur within 2 weeks prior to randomization and/or during the study.
19. Are taking or require oral or injectable (eg, intraarticular, intramuscular or intravenous) corticosteroids for any condition. (Must be discontinued for at least 4 weeks prior to first dose of study drug).
20. Have been vaccinated with live or attenuated live vaccine within the 6 weeks prior to the first dose of study drug or expects to be vaccinated with these vaccines during treatment, or within the 8 weeks following the last dose of study drug. (For further information regarding avoidance of household contacts who may be vaccinated see [Section 5.3.2](#)).

21. Require treatment with prohibited concomitant medications(s) (see [Section 6.5](#)) or have received a prohibited concomitant medication/dietary supplement within 7 days or 5 half-lives (whichever is longer) prior to the first dose of study drug. Details include specific discontinuation recommendations and, additional details are found in [Appendix 8](#).
22. Previous administration with an investigational drug within 30 days (or as determined by the local requirement) or 5 half-lives preceding the first dose of investigational product used in this study (whichever is longer).

Diagnostic Assessments:

23. Known history of incompletely treated hepatitis B or C, or human immunodeficiency virus (HIV) based on documented history with positive serological test, or positive HIV serological test at screening.
 - Participants who are hepatitis C antibody (HCVAb) positive require further testing with Hepatitis C virus (HCV) ribonucleic acid (RNA) Polymerase chain reaction (PCR) may be eligible if HCV RNA PCR is negative.
 - Participants who are hepatitis B surface antigen (HBsAg) negative and hepatitis B core antibody (HBcAb) positive will be reflex tested for Hepatitis B Surface Antibody (HBsAb). If HBsAb is positive, participant may be eligible. If HBsAb is negative, the participant is not eligible. This reflex test applies to all countries except Japan.
 - Participants who are negative for all three serology tests may be eligible.
 - Participants who are HBsAg positive are not eligible.
 - In **Japan ONLY**, *all* participants will undergo testing for all three tests HBsAg, HBcAb, and HBsAb during Screening.
 - Participants who have negative HBsAg, positive HBcAb, and negative HBsAb are not eligible.
 - Participants who have negative HBsAg, negative HBcAb and positive HBsAb and provide a documentation of prior Hepatitis B Virus (HBV) vaccination may be eligible and will not require HBV DNA monitoring during the study.
 - Participants who have negative HBsAg, negative HBcAb and positive HBsAb *without* documentation of prior HBV vaccination, and who have negative HBsAg, positive HBcAb and positive HBsAb are required to undergo HBV DNA reflex testing.
 - Participants with detectable HBV DNA are not eligible.

- Participants without detectable HBV DNA may be eligible. If enrolled, HBV DNA will be assessed at Weeks 12 (Investigational Treatment Period), Weeks 24, 36 (Extension Treatment Period) and ET (if applicable).
24. Screening or baseline standard 12-lead electrocardiogram (ECG) that demonstrates clinically relevant abnormalities that may affect participant safety or interpretation of study results (eg, baseline corrected QT [QTc] interval >450 millisecond (msec), complete left bundle branch block [LBBB], signs of an acute or indeterminate-age myocardial infarction, ST-T interval changes suggestive of myocardial ischemia, second- or third-degree atrioventricular [AV] block, or serious bradyarrhythmias or tachyarrhythmias). If the baseline uncorrected QT interval is >450 msec, this interval should be rate-corrected using the Fridericia method and the resulting corrected QT interval by Fridericia (QTcF) should be used for decision making and reporting. If QTc exceeds 450 msec, or QRS exceeds 120 msec, the ECG should be repeated 2 more times and the average of the 3 QTc or QRS values should be used to determine the participant's eligibility. Computer-interpreted ECGs should be over read by a physician experienced in reading ECGs before excluding participants.
25. Participants with ANY of the following abnormalities in clinical laboratory tests at screening, as assessed by the study-specific laboratory and confirmed by a single repeat, if deemed necessary:
- Hemoglobin <11.0 g/dL or hematocrit <30% (<0.30 v/v);
 - White blood cell count <3.0 x 10⁹/L (<3000 mm³);
 - Absolute lymphocyte count of <1.0 x 10⁹/L (<1000/mm³);
 - Absolute neutrophil count of <1.5 x 10⁹/L (<1500/mm³);
 - Platelet count <100 x 10⁹/L (<100,000/mm³);
 - eGFR (estimated glomerular filtration rate) <60 mL/min/1.73 m² using serum creatinine based on the Chronic Kidney Disease Epidemiology Collaboration (CKD EPI) calculation;
 - Aspartate aminotransferase (AST) or alanine aminotransferase (ALT) values >2 times the upper limit of normal (ULN);
 - Total bilirubin ≥1.5 times the ULN; participants with a history of Gilbert's syndrome may have a direct bilirubin measured and would be eligible for this study provided the direct bilirubin is <ULN.

In the opinion of the investigator or sponsor, any uncontrolled clinically significant laboratory abnormality that would affect interpretation of study data or the participant's participation in the study.

Other Exclusions:

26. Investigator site staff members directly involved in the conduct of the study and their family members, site staff members otherwise supervised by the investigator, or Sponsor employees, including their family members, directly involved in the conduct of the study.
27. Have a history of alcohol or substance abuse, unless in full remission for greater than 6 months prior to Day 1.

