7. DISCONTINUATION OF STUDY INTERVENTION AND PARTICIPANT DISCONTINUATION/WITHDRAWAL

7.1. Discontinuation of Study Intervention

In rare instances, it may be necessary for a participant to permanently discontinue the investigational product. Per the study estimands, if investigational product is permanently discontinued, the participant will proceed to Early Termination per [Schedule of Activities](#). The site will inform sponsor medical monitor or sponsor clinician if the below criteria for permanent discontinuation of the IP are triggered.

Any participant meeting discontinuation criteria must have an Early Termination visit with their first visit occurring 1 week after their last dose whenever possible and continue visits per Investigator's discretion until the event has returned to normal or baseline levels or is deemed clinically stable.

The only exception to this is when a participant specifically withdraws consent for any further contact with him or her or persons previously authorized by the participant to provide this information.

Note that discontinuation of the investigational product does not represent withdrawal from the study.

Participants experiencing a thrombotic event as part of a serious adverse event must be discontinued from further IP administration and referred to a specialist for further evaluation of possible hypercoagulable state, as per local guidelines.

ECG Changes

A participant who meets either bulleted criterion below based on the average of triplicate ECG readings will be withdrawn from the IP administration.

- QTcF >500 msec;
- Change from baseline: QTc >60 msec.

If a clinically significant finding is identified (including, but not limited to, changes from baseline in QTcF after enrollment), the investigator or qualified designee will determine if the participant can continue in the study and if any change in participant management is needed. This review of the ECG printed at the time of collection must be documented. Any new clinically relevant finding should be reported as an AE.

Laboratory Abnormalities

All the following laboratory abnormalities require discontinuation if they are confirmed.
Confirmation through re-testing should occur within 48 hours:

Laboratory Variable	Laboratory Value
Hematology	
Absolute Neutrophil Count	<1000/mm ³ ; <1.0 x10 ⁹ /L
Hemoglobin	<10.0 g/dL; <6.2 mmol/L; <100 g/L
Platelet count	<75,000/mm ³ ; <75.0x10 ⁹ /L
Lymphocytes	<500/mm ³ ; <0.5x10 ⁹ /L
Chemistry	
AST ^a	>3x ULN

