8.2.3. Electrocardiograms

Six singlicate standard 12-Lead ECGs should be collected at times specified in the [SoA](#) section of this protocol using an ECG machine that automatically calculates the heart rate and measures pulse rate (PR), QT, and QTc intervals and QRS complex. All scheduled ECGs should be performed after the participant has rested quietly for at least 10 minutes. Consistent methods across visits is recommended.

ECGs should be performed before laboratory blood collection, BP, and pulse rate.

To ensure safety of the participants, a qualified individual (eg, sub-investigator) at the investigator site will make comparisons to baseline measurements taken at baseline. A copy of the ECG should be available as source documents for review. ECGs will be read locally during the dosing period.

If a postdose QTc interval remains ≥ 30 msec from the baseline **and** is >450 msec; or b) an absolute QTc value is ≥ 500 msec for any scheduled ECG for greater than 4 hours (or sooner, at the discretion of the investigator), or QTc intervals get progressively longer, the participant should undergo continuous ECG monitoring. A cardiologist should be consulted if QTc intervals do not return to less than the criterion listed above after 8 hours of monitoring (or sooner, at the discretion of the investigator).

In some cases, it may be appropriate to repeat abnormal ECGs to rule out improper lead placement as contributing to the ECG abnormality. It is important that leads be placed in the same positions each time in order to achieve precise ECG recordings. If a machine-read QTc value is prolonged, as defined above, repeat measurements may not be necessary if a qualified medical provider's interpretation determines that the QTc values are in the acceptable range.

ECG values of potential clinical concern are listed in [Appendix 7](#).

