10.7. Appendix 7: ECG Findings of Potential Clinical Concern

ECG Findings That May Qualify as Adverse Events (AEs)

- Marked sinus bradycardia (rate <40 beats per minute (bpm)) lasting minutes.
- New PR interval prolongation >280 msec.
- New prolongation of QTcF to >480 msec (absolute) or by ≥ 60 msec from baseline.
- New-onset atrial flutter or fibrillation, with controlled ventricular response rate: ie, rate <120 bpm.
- New-onset type I second-degree (Wenckebach) AV block of >30 seconds' duration.
- Frequent premature ventricular contraction/complexes [per Abbreviations] (PVCs), triplets, or short intervals (<30 seconds) of consecutive ventricular complexes.

ECG Findings That May Qualify as Serious Adverse Events (SAEs)

- QTcF prolongation >500 msec.
- New ST-T changes suggestive of myocardial ischemia.
- New-onset left bundle branch block (QRS >120 msec).
- New-onset right bundle branch block (QRS >120 msec).
- Symptomatic bradycardia.
- Asystole:
 - In awake, symptom-free patients in sinus rhythm, with documented periods of asystole ≥ 3.0 seconds or any escape rate <40 bpm, or with an escape rhythm that is below the AV node;
 - In awake, symptom-free patients with atrial fibrillation and bradycardia with 1 or more pauses of at least 5 seconds or longer;
 - Atrial flutter or fibrillation, with rapid ventricular response rate: rapid = rate >120 bpm.
- Sustained supraventricular tachycardia (rate >120 bpm) ("sustained" = short duration with relevant symptoms or lasting >1 minute).
- Ventricular rhythms >30 seconds' duration, including idioventricular rhythm (rate <40 bpm), accelerated idioventricular rhythm ($40 < x < 100$), and

monomorphic/polymorphic ventricular tachycardia >100 bpm (such as torsades de pointes).
 
• Type II second-degree (Mobitz II) AV block.• Complete (third-degree) heart block.
ECG Findings That Qualify as Serious Adverse Events

• Change in pattern suggestive of new myocardial infarction.• Sustained ventricular tachyarrhythmias (>30 seconds' duration).• Second- or third-degree AV block requiring pacemaker placement.• Asystolic pauses requiring pacemaker placement.• Atrial flutter or fibrillation with rapid ventricular response requiring cardioversion.• Ventricular fibrillation/flutter.• At the discretion of the investigator, any arrhythmia classified as an adverse experience.

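### Criterion 24 ties the Fridericia correction to a raw baseline QT above 450 msec and no formula is named otherwise, so QTc baselines and changes may rest on different corrections

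*Protocol*

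**What the plan says.** Criterion 24 (Protocol Section 5.2) gives, as an example of an exclusionary ECG finding, "baseline corrected QT [QTc] interval >450 millisecond (msec", without naming a correction. It continues: "If the baseline uncorrected QT interval is >450 msec, this interval should be rate-corrected using the Fridericia method", and then "the resulting corrected QT interval by Fridericia (QTcF) should be used for decision making and reporting". A QTc above 450 msec calls for two further ECGs, and "the average of the 3 QTc or QRS values should be used to determine the participant's eligibility". That step names no formula and sets no condition on the raw QT.

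Section 8.2.3 obtains the intervals "using an ECG machine that automatically calculates the heart rate and measures pulse rate (PR), QT, and QTc intervals and QRS complex", and adds "ECGs will be read locally during the dosing period". It does not say how the machine corrects QT.

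The terms differ elsewhere:

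- **Section 7.1:** the absolute withdrawal limit of 500 msec is in QTcF. The second limit reads "Change from baseline: QTc >60 msec". The paragraph after it speaks of change from baseline in QTcF.
- **Section 9.4.2.1:** the summaries and the prolongation categories (including increases of 30-60 and >60 msec) are in QTc. The listing of values above 500 msec is in QTcF.
- **Appendix 7:** "New prolongation of QTcF to >480 msec (absolute) or by ≥ 60 msec from baseline".
- **SAP Sections 3.1.2 and 6.3:** QTc only. In the visible SAP text, QTcF appears only in the list of abbreviations.

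No visible passage in either document says that every QTc, or every baseline QTc, is Fridericia-corrected.

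**The concern.** Whether QT needs rate correction depends on heart rate, not on the size of the raw interval. A rule that calls for Fridericia only above a raw QT of 450 msec therefore lets the raw QT decide which correction a participant's baseline carries. The condition is written for the baseline ECG only, so a triggered participant has a QTcF baseline but, on the wording, later values from the machine.

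That baseline is the reference for the change limit in Section 7.1, the monitoring criterion in Section 8.2.3 (at least 30 msec above baseline and above 450 msec), the change criterion in Appendix 7 and the increase categories in Section 9.4.2.1. Clinically significant ECG change is a secondary safety endpoint of the 16-week period and a primary endpoint of the Extension Treatment Period. If baseline and post-dose values carry different corrections, a tabulated change partly measures the formula and the heart rate rather than the drug. Local reading in a multicenter study means the formula could also differ between sites.

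**Working it through.** **Inputs.** From the documents: the raw-QT trigger of 450 msec and the QTc limit of 450 msec (Section 5.2), the increase categories 30-60 and >60 msec (Section 9.4.2.1), and the monitoring criterion (Section 8.2.3). The heart rates and QT values below are illustrative. Bazett as the machine formula is an assumption. The plan states no figure to reproduce.

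**Formulas.** Fridericia: QTcF = QT × (HR/60)^(1/3). Bazett: QTcB = QT × (HR/60)^(1/2).

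**Step 1: does screening miss anyone with QTcF above 450 msec?**

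| QT (msec) | HR (bpm) | Trigger met? | QTcF | QTcB |
|---|---|---|---|---|
| 430 | 70 | no | 452.7 | 464.5 |
| 410 | 80 | no | 451.3 | 473.4 |
| 400 | 90 | no | 457.9 | 489.9 |
| 420 | 90 | no | 480.8 | 514.4 |
| 480 | 50 | yes | 451.7 | 438.2 |

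Above 60 bpm QTcB exceeds QTcF, so anyone there with QTcF above 450 is flagged by the general limit under either formula. Below 60 bpm, QTcF above 450 requires raw QT above 450, so the trigger fires and QTcF is used. Under Fridericia or Bazett machines, nobody with QTcF above 450 is missed. The opposite can occur: QT 400 at 80 bpm is 461.9 by Bazett but 440.3 by Fridericia.

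**Step 2: which eligible participants have a triggered QTcF baseline?** They need QT > 450 and QTcF ≤ 450, so (HR/60)^(1/3) ≤ 450/QT < 1, which means HR < 60 bpm.

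**Step 3: size of the baseline mismatch in that group, if the machine reports Bazett.**

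- QT 460 at 55 bpm: QTcF 446.8, QTcB 440.4, difference 6.4 msec.
- QT 460 at 50 bpm: QTcF 432.9, QTcB 419.9, difference 13.0 msec.

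**Step 4: effect on a change from baseline.** Take a baseline of QT 460 at 50 bpm and a later ECG of QT 380 at 90 bpm.

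- Later QTcF = 380 × 1.5^(1/3) = 435.0. Later QTcB = 380 × 1.5^(1/2) = 465.4.
- QTcF baseline against a Bazett post-dose value: 465.4 − 432.9 = +32.5 msec. This falls in the 30-60 category and passes both numerical thresholds in Section 8.2.3.
- QTcF at both times: 435.0 − 432.9 = +2.1 msec, in no category.
- Bazett at both times: 465.4 − 419.9 = +45.5 msec, also in the 30-60 category.

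The last line shows that using the same formula at both visits is not enough. The formula has to be named.

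**The case against.** A reader might infer that the trigger lets participants with fast heart rates and long corrected intervals into the trial. The documents do not support this. The QTc limit and the repeat rule in criterion 24 do not depend on raw QT, and Step 1 shows that those participants are flagged. What the trigger omits is the instruction to use Fridericia, not QTc screening.

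A reader might also put the baseline mismatch at 20 to 30 msec, up to half of the 60 msec change limit. That is the Bazett-Fridericia gap for QT 380 at 80 to 90 bpm (20.5 and 30.4 msec). No eligible participant has a triggered baseline at those rates: a raw QT above 450 gives QTcF above 495 at 80 bpm.

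The best defence is that the protocol implies QTcF throughout. Section 7.1 refers to QTcF changes from baseline. The change criterion in Appendix 7 needs a QTcF baseline for every participant. Section 9.4.2.1 lists QTcF above 500 msec, and Section 8.2.3 recommends consistent methods across visits. This carries weight: a site or programmer could derive QTcF for all ECGs, and the mix of corrections follows from literal wording rather than from an explicit instruction. But no visible text directs that derivation, and criterion 24 makes it conditional.

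It is also fair that the ECG results are descriptive and that the numerical harm depends on an undocumented machine formula.

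**Conclusion.** The point holds as a defect in the definition of baseline QTc and of the QTc change tables, not as a gap in screening. Read literally, baselines of eligible participants with heart rate below 60 bpm and raw QT above 450 msec are QTcF, while other baselines and post-dose values are whatever the local machine reports.

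If that is Bazett, the direct baseline discrepancy is modest, about 6 to 13 msec in the examples. A mixed comparison with a later ECG at a faster rate can still move a participant into the 30-60 msec category (+32.5 against about +2 msec in QTcF). If all machines report QTcF, the numerical effect is nil and only the inconsistent wording remains.

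The documents do not show how many participants would meet the trigger. The consequence is confined to eligibility consistency, the QTc change criteria and the ECG safety tables. It should be corrected because the remedy costs almost nothing.

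**What to change.** For the analysis, state in Protocol Section 9.4.2.1 and in the ECG sections of the SAP (6.3 and 6.8.4): QTcF is derived as QT × (HR/60)^(1/3) from the QT and heart rate recorded on each ECG, whatever the raw QT, and this value is used for the baseline, for changes from baseline and for the prolongation categories.

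Separately, the sponsor should reconcile the QTc and QTcF wording in criterion 24, Sections 7.1 and 8.2.3 and Appendix 7 to one named definition. This review does not say which eligibility or withdrawal rule is right, and it proposes no change to any threshold.

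The cost is one derivation in the programming and wording edits. Section 9.4.2.1 already summarizes QT and heart rate, so no new procedure or data are needed. The downside is that some tabulated values may differ from the machine printout that the site saw.
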